2. Each equivalent active dose will look identical to its corresponding placebo. Because the intent of the study is NOT to conceal the timing of dose changes from subjects, it has been strongly recommended that different colored capsules for different dose levels (keeping active/placebo pairs identically matched, of course) be maintained. Based on prior experience, not color-coding dose levels (and similarly placebo) will greatly increase the chance for medication errors. Given it is very common for manufactured medications to have different colors at different dose levels, most subjects will likely be familiar with this practice. The alternative would be for all active capsules to contain 0.125 mg of pramipexole and have subjects take more capsules for a higher dose level. Those subjects who end up at the highest dose level (0.75mg) would then have to take three capsules per dose.
3. IDS' operating hours are Monday through Friday from approximately 8:00 to 4:30, excluding UNMH holidays. Dispensing times will occur during these periods. Most days, staffing consists of an IDS pharmacy technician ([name]) and an IDS pharmacist. There are two trained IDS backup pharmacists ([name] and [name]) to cover [name]'s leave periods. Accordingly, trained IDS staff will be available during the IDS operating hours barring rare exceptions when, for example, the IDS pharmacy technician is out on vacation and the IDS pharmacist needs leave for a meeting. Dispensing during evenings, nights, weekends, and holidays, will not occur.

## **14. Provisions to Monitor the Data to Ensure the Safety of Subjects**

*This section is required when research involves more than Minimal Risk to subjects.*

*Describe:*

### Contact Information

Standard procedures, which are comprised of in-person description of the study and consent, completion of the Brief Pain Inventory (short form), and electronic communication, which is used to track pain scores via phone call on weeks 1 and 3. We will identify all subjects with a sequentially assigned subject ID number and subject initials. The subject ID number will be utilized for data collection (questionnaires, blood specimens, and database entry). To ensure subject confidentiality, no names, social security numbers, or UNM pain clinic numbers will be included in any communication external to UNM. Names, addresses, telephone numbers, and any other information needed for recruitment, study involvement, and tracking will be obtained and maintained locally by the study staff (UNM CTSC Clinical Research Coordinator). All computer files and systems will be password protected and accessible by authorized Informatics study staff only (CTSC Analyst/Programmer).

**Data Safety:** The risk of breach of confidentiality is considered to be similar or even less than a data safety compromise of non-research clinical electronic health records. To minimize potential breach of confidentiality, all electronic data will be maintained in a password-protected database to which only study staff with a legitimate need will have access. All paper documentation will be kept in a secure file cabinet in a locked office. The CRC will be responsible for keeping the data in a password protected database with hard copies of the BPI kept in a locked file cabinet in the CTSC during the study period. Monitoring will occur daily or when needed while enrolling subjects and collecting BPI scores. After the study period, Drs. [name] and [name] will maintain the study records (electronic version of the BPI scores, mRNA and protein analysis from cell-based assays) in [name] office in a password protected database and hard copies of the BPI will be kept in a locked file cabinet in a locked room ([name] and [name] offices).

### Safety Monitoring Plan:

While there are no contraindications associated with pramipexole, the collection and reporting of adverse are as follows:

The collection and reporting of adverse events will occur at: (1) the time of the phone conversation at the end of weeks 1 and 3 with the CRC who will collect the Brief Pain Inventory scores, (2) at the end of week 2, the time of the mid-term in-person meeting with the CRC when the subject will provide the scores of the BPI for that week and will pick up drug dispense #2, (3) At the final in-person with the CRC, at the termination of the study at week 4, and (4) at any point during the study when the subject calls the CRC to report an adverse event or when the subject calls [name]. All adverse events will be recorded by the CRC and kept with the subject's study records.

Symptomatic orthostatic hypotension and other adverse reactions will be monitored during dose escalation during weeks 1-2, as well as throughout the 4-week study, as part of the routine contact with participants.

The HRRC will be notified as per usual rules within five business days after the PI becomes aware of any severe adverse events, as defined by the Common Terminology Criteria for Adverse Events (CTCAE) version 5.0, published 11/27/2017 by the National Cancer Institute. The CTCAE defines adverse events of grade 3 or higher as “severe.”

Safety monitoring will occur in two tracks. In one track, monitoring will occur as part of the routine (weekly) study-related contact. Study personnel will include screening for adverse events as noted in the included script. The PI will be notified promptly of any moderate or severe adverse events identified in this screening process. All screening information will be provided to the PI for review in the second track of the monitoring procedure, and for entry in a Non-Reportable Log, as appropriate.

The second track of safety monitoring will be an interim review conducted shortly (within one week) after enrollment of the 15th participant. All relevant study information, including but not limited to pain and dosage data, any adverse events identified in screening (regardless of CTCAE grade), and any direct adverse-event reports to investigator [name], will be included in this review. PI [name] will conduct this review with assistance from investigators [name] and [name]. The HRRC will be notified if adverse events of CTCAE grade  $\geq 2$  have been identified in three or more patients in the active (pramipexole) arm at the time of this review. As noted above, the HRRC will be notified within five business days of any adverse events of grade 3 or higher, regardless of timing with respect to this interim review.

Stopping rules: Enrollment will be at least temporarily suspended if any of the following conditions are met:

- Instructions from the HRRC to suspend or terminate enrollment.
- A second adverse event of CTCAE grade 3 or higher among study participants. As with any first one, this event would be reported to the HRRC.
- Any event that, in the opinion of the PI, represents substantial unanticipated risk (i.e. a risk not included in the FDA pramipexole package insert or consent documentation) to study participants.

After any suspension, enrollment would only be resumed on instructions from the HRRC.

If enrollment is suspended, study-related treatment will continue as normal for any active study participants, except in the case of the third (substantial unanticipated risk) bullet point above. If study enrollment is suspended for that reason, participants will be advised to taper off or terminate study drug use as soon as possible.

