2. Advanced PD with levodopa: postural (orthostatic) hypotension, dyskinesia, extrapyramidal syndrome, insomnia, dizziness, hallucinations, accidental injury, dream abnormalities, confusion, constipation, asthenia, somnolence, dystonia, gait abnormality, hypertonia, dry mouth, amnesia, and urinary frequency.
3. RLS: nausea, somnolence, fatigue, and headache

In the event of an adverse event, the HRRC will be notified. An adverse event case report from will be completed. The CRC will notify [name] and [name] as well as the appropriate personnel in the HRRC. It is important to note that a standardized form will be used for adverse event reporting. The form will ask the following questions:

1. Have you experienced any unusual events since you were last seen here? If yes, the CRC will probe further and ask:
2. What exactly did you experience?
3. Did you seek treatment for this experience?
4. Were you given any medications. What was the dose and date started? Are you still taking this medication? If no, when did you stop taking this medications? and should specifically
5. Have you been feeling dizzy and have you experienced any falls?

In addition, the opinion of [name] will note on the adverse event case report from if this adverse event was associated with the study drug, pramipexole.

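### The documents conflict on whether the coordinator or the pharmacy uses the randomization table, and the interim safety rule does not say who supplies the arm count

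*Combined protocol and SAP*

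**What the plan says.** **Who uses the table.** Section 4.1 says that a table covering all subjects will serve the Clinical Research Coordinator as a template when drug is handed out at consent. The same sentence appears in Section 14 (Recruitment of Subjects) and Section 19. Section 9 lists dispensing of pramipexole or placebo among the coordinator's tasks. Section 3.2, under the prompt on blinding, has subjects pick up capsules from the hospital's clinical pharmacy, which dispenses active or placebo. Section 31 has the research pharmacy dispense, guided by the table.

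**What else the coordinator does.** Section 14 has adverse events collected at phone contacts in weeks 1 and 3 "with the CRC who will collect the Brief Pain Inventory scores", and at the visits in weeks 2 and 4. The coordinator records all adverse events. Section 7.4 makes the Brief Pain Inventory (BPI) the primary endpoint.

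**What is masked.** Section 13 describes active and placebo capsules of identical appearance at each dose level. Section 3.2 does not say which roles are blinded.

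**Interim review.** Within one week of the 15th enrollment, the PI and two investigators review the data. "All relevant study information, including but not limited to pain and dosage data" goes into that review, along with all adverse events. The HRRC is notified if events of grade 2 or higher "have been identified in three or more patients in the active (pramipexole) arm at the time of this review". The suspension rule in the same section is not by arm: "A second adverse event of CTCAE grade 3 or higher among study participants".

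**Event reporting.** Section 14 (Safety Monitoring Plan) sends screening information to the PI "for entry in a Non-Reportable Log, as appropriate" and sets grade-based rules for telling the HRRC. Later in Section 14, after the list of drug risks, a sentence has no grade limit: "In the event of an adverse event, the HRRC will be notified".

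**The concern.** Matched capsules keep subjects masked, but they do nothing for a person who holds the list that says which subject gets which capsule. If the coordinator works from the table, the person who takes pain scores by phone and asks about adverse events may know every arm from the start. That could colour how scores are elicited and how events are probed and written down. The coordinator also obtains consent (Section 24), so a list covering later subjects would show upcoming assignments too.

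The interim rule is a smaller matter. It cannot be applied without some arm information once enough subjects are affected, and the review falls while 15 to 30 subjects are still to be recruited (30 − 15 and 45 − 15, from Section 5.5). No pause in enrollment is described. What could be affected is judgement that follows the review: later recruitment, or the opinion on "if this adverse event was associated with the study drug, pramipexole".

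**Working it through.** **Step 1. Set the dispensing passages side by side.**

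| Section | Who dispenses | Who uses the table |
|---|---|---|
| 4.1, 14 (Recruitment of Subjects), 19 | Coordinator | Coordinator |
| 9 | Coordinator | Not stated |
| 3.2 | Pharmacy | Table mentioned, user not stated |
| 31 | Pharmacy | Pharmacy |

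A pharmacy could fill coded packs that the coordinator passes on, which would reconcile the act of handing out. It would not reconcile use of the table: Section 4.1 describes it as a table of pramipexole versus placebo and gives it to the coordinator. This part needs no event-rate assumption.

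**Step 2. When does the interim rule need arm information?** If fewer than three of the 15 are affected, the active arm cannot reach three and no label is needed. Let X be the number of the first 15 with an event of grade 2 or higher, Y the number in the active arm, and Z the number on placebo. The documents give neither an allocation ratio nor a rate of such events. I assume 1:1 allocation (7 or 8 active), independent events, full follow-up of all 15 (which overstates the counts somewhat), and the same rate p in both arms.

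- Arm information needed: P(X ≥ 3) = 1 − P(0) − P(1) − P(2), with X ~ Bin(15, p). At p = 0.05: 1 − 0.463 − 0.366 − 0.135 = 0.036.
- Affected subjects in such reviews: E[X | X ≥ 3].
- Rule met: P(Y ≥ 3), with Y ~ Bin(7 or 8, p).
- An exact active-arm total identifies everyone affected only if all are in one arm: [P(Y ≥ 3)P(Z = 0) + P(Y = 0)P(Z ≥ 3)] / P(X ≥ 3). At p = 0.05 with 8 active: (0.0058 × 0.698 + 0.663 × 0.0038) / 0.0362 = 0.18.

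| Assumed p | Arm information needed | Mean affected, given needed | Rule met | Total alone identifies all, given needed |
|---|---|---|---|---|
| 5% | 0.036 | 3.2 | 0.004–0.006 | 0.18 |
| 10% | 0.184 | 3.4 | 0.026–0.038 | 0.16 |
| 20% | 0.602 | 4.0 | 0.148–0.203 | 0.11 |
| 30% | 0.873 | 4.9 | 0.353–0.448 | 0.07 |

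**Step 3. Sensitivity.** The only nearby rates in the documents are for somnolence, 6% versus 3% (Section 14, doses of 0.25–0.75 mg in restless legs trials). They cover one event at any grade, so they are not an overall rate of grade 2 or higher. Put in as if they were, they give arm information needed in 2.6–2.9% of reviews and the rule met in 0.6–1.0%. With a placebo rate half the active rate (active 10%, 20%, 30%), arm information is needed in 9–10%, 38–41% and 68–71%. A total alone then identifies everyone somewhat more often than in the table, because the affected subjects cluster in one arm.

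**Step 4. What remains if only a yes or no goes to the HRRC?** A visible HRRC action identifies every affected subject's arm only when exactly three are affected and all are active: P(Y = 3) × P(Z = 0). At equal rates of 5%, 10%, 20% and 30% this is 0.2–0.4%, 1.0–1.6%, 1.9–3.1% and 1.3–2.1% of reviews. With the placebo rate at half of 10–30% it is 1.5–8.2%.

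**The case against.** A reader might infer that the interim review will open the arms of three to five subjects to the PI and two investigators. The documents do not support that. The rule needs a count, not subject-level codes. The figure of 3.2 to 4.9 holds only when three or more are affected and every affected subject is decoded to the reviewers, and the 20% and 30% event rates behind its upper part are assumptions.

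The documents also never say that the investigators are blinded; that is inferred from the placebo control and the matched capsules. A labelled safety look by a small team without a separate monitoring board is a legitimate choice. The names are redacted, so it cannot be shown that a reviewer is also the person who recruits or who judges causality. All of this stands, and it makes the interim rule the lesser part of the point.

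A reader might also infer that the coordinator will in fact be unblinded, or that the quarterly meetings in Section 9 show pain scores by arm. The first is one of two conflicting descriptions, not a settled procedure. For the second, Section 9 mentions preliminary pain findings but not by arm.

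Consequences have limits too. Subjects complete the BPI themselves, blood assays wait until all subjects have finished (Sections 12 and 27.4), and the review opens no later subject's label. None of this resolves the conflict over the table.

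**Conclusion.** The concern holds, led by custody of the table. Sections 4.1, 9, 14 and 19 cannot be followed together with Section 31 as written, and under the first set the collector of the primary endpoint and of adverse events may know all assignments. The effect on the BPI result cannot be sized from the documents.

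The interim rule is a secondary gap. Arm information would be needed in about 4% to 87% of reviews at assumed equal rates of 5% to 30%, and in about 3% at the somnolence rates. An exact total alone would identify all affected subjects' arms in about 7% to 18% of such reviews at equal rates; only subject-level decoding would do so every time. These figures rest on 1:1 allocation, independence and assumed rates.

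The HRRC notification sentence without a grade limit does not fit the Non-Reportable Log or the grade-based rules. It is a separate reporting inconsistency, not a blinding matter. The whole point merits a change before recruitment, with medium confidence.

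**What to change.** 1. Reconcile Sections 3.2 and 31 with Sections 4.1, 9, 14 and 19 so that the pharmacy alone holds the table and the coordinator handles coded supplies only. State in Section 3.2 which roles are blinded.
2. In the interim review text of Section 14, have the research pharmacist match the list of affected subjects to the table when three or more are affected, and report to the HRRC only whether the active-arm count is three or more. The threshold, the reporting of grade 3 or higher and the stopping rules stay unchanged. If a labelled look is intended, say so and name the role that sees the labels.
3. Separately, reconcile the HRRC notification sentence that has no grade limit with the Safety Monitoring Plan, so that it is clear which events go to the HRRC and when.

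The cost is protocol wording, coded supplies and at most one short task for a pharmacy that Section 13 shows is already staffed. The downside is that the team sees no arm-level safety data unless the HRRC asks for it, and the documents describe no separate monitoring board. An HRRC action can still reveal arms when exactly three subjects are affected, so the change reduces that exposure without removing it.

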**Dose escalation risks**

Dose titration will increase by double if efficacy has not been achieved by the end of one week at the lower initial dose. A dose of 0.125 mg pramipexole once per night for 1 week is initiated for all subjects. At the end of week one, subjects will either increase the dose by double, 0.25 mg if pain relief is not satisfactory, or will remain at 0.125 mg if relief is satisfactory. A 2nd titration may occur at the end of week 2, with the dose escalating from 0.25 mg to 0.75 mg per night. Please see flow chart indicating the 'Dispensing Guideline', as an illustration.

Safety will be monitored either at the time the CRC asks the subject to provide their scores on the Brief Pain Inventory, or when the subject calls [name] reporting adverse experiences as indicated in safety endpoints. Upon consent, subjects will be instructed to call [name] should any adverse experiences noted in the 'safety endpoints' occur during the study period. After the study period is terminated, subjects will continue to see [name] in follow-up visits as needed.

All risks associated with pramipexole (Mirapex; Boehringer Ingelheim Pharmaceuticals) according to the manufacturer are:

1. Falling asleep during activities of daily living. Sudden onset of sleep may occur without warning. Somnolence is a common occurrence in patients receiving pramipexole at doses above 1.5 mg/day (0.5 mg three times a day). In controlled clinical trials in Restless Leg Syndrome, patients treated with MIRAPEX tablets at doses of 0.25-0.75 mg once a day, the incidence of somnolence was 6% compared to an incidence of 3% for placebo-treated patients.

2. Symptomatic orthostatic hypotension: Dopamine agonists, in clinical studies and clinical experience, appear to impair the systemic regulation of blood pressure, with resulting orthostatic hypotension, especially during dose escalation. Despite clear orthostatic effects in normal volunteers, the reported incidence of clinically significant orthostatic hypotension was not greater among those assigned to pramipexole tablets than among those assigned to placebo.

Symptomatic orthostatic hypotension will be monitored during dose escalation during weeks 1-2, as well as throughout the 4-week study. Monitoring will occur as detailed in “Collection and Reporting of Adverse Events”.

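### After a second grade 3 or higher event enrolment stops, but active subjects may still take their next dose increase without any required decision on whether escalation should continue

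*Combined protocol and SAP*

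**What the plan says.** **The trigger.** Under Stopping rules in Section 14, one of three conditions that suspend enrolment is "A second adverse event of CTCAE grade 3 or higher among study participants". It is not limited by arm or by cause. The other two are an HRRC instruction and a substantial risk that the PI judges unanticipated, meaning one in neither the package insert nor the consent documentation.

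**What follows for subjects on treatment.** During a suspension, "study-related treatment will continue as normal for any active study participants", "except in the case of the third (substantial unanticipated risk) bullet point above". Only in that excepted case are subjects told to taper or stop. The HRRC's say after a suspension concerns restarting enrolment.

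**What normal treatment is.** Under Dose escalation risks: "At the end of week one, subjects will either increase the dose by double, 0.25 mg if pain relief is not satisfactory". Sections 12, 13 and 31 and Potential Risks likewise describe increases at the ends of weeks 1, 2 and 3, driven by pain relief.

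**Notice and review.** The Safety Monitoring Plan has the PI told promptly of moderate or severe events, and the HRRC notified "within five business days after the PI becomes aware of any severe adverse events". One aggregate review is scheduled. It is tied to the 15th enrolment, not to events, and it covers study information "including but not limited to pain and dosage data".

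**The concern.** The protocol treats two severe events as reason enough to stop exposing new people. For risks already listed, such as sudden sleep, orthostatic hypotension or hallucinations, the same text lets subjects already on study drug move to a higher dose, and nobody has to consider first whether the events bear on that. Dose is the natural thing to look at, because Dose escalation risks says that orthostatic effects arise particularly while the dose is being raised. At stake is the safety of a few subjects for up to one titration interval at a time. The trial's estimate of efficacy is not at issue.

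**Working it through.** The plan gives no figure for this rule. The check is a reading of the text followed by simple arithmetic on timing and scale.

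**1. Does another provision require a decision about other subjects' next dose?**

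| Provision | What it requires | Decision about other subjects' dose? |
|---|---|---|
| Section 7.5; Section 14, urges and hallucinations | Dose reduced or stopped, or reduction considered, in the affected subject | No |
| Safety Monitoring Plan, weekly screening | Each subject asked about own events at each weekly contact | No |
| Safety Monitoring Plan, PI notice | PI told promptly | No |
| Section 14, adverse event form | Coordinator notifies two investigators and the HRRC; opinion on drug relatedness recorded | No |
| Section 9.5 | Physician responsible for medical decisions | General duty, no trigger |
| Section 24 | Investigators may end participation | Discretionary |
| Section 9, team meetings | Every three months | Not event-driven |

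**2. Timing.** Titration points are 7 days apart. Five business days is 7 calendar days if the PI learns of the event on a weekday (6 from a Saturday, 5 from a Sunday, longer with a holiday). If a subject's next titration point is equally likely on days 1 to 7, then 6/7 = 86% of subjects in weeks 1-3 reach it before a 7-day deadline and all reach it by the deadline. This is the outer limit for notice. No time is stated for an HRRC response.

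**3. Supply.** The first dispense is 7 × 1 + 7 × 2 = 21 Red. The second is 21 Red on the same sum, or 7 × 2 + 7 × 3 = 35 Green. These match Section 12. Increases at the ends of weeks 1 and 3 can thus follow a phone contact with capsules already in hand.

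**4. How many subjects.** Inputs are 30 subjects with complete data and up to 45 recruited (Section 5), and 10-11 months of enrolment (Section 6), which is 43.3-47.7 weeks at 52/12 weeks per month. Assuming even accrual, other subjects in weeks 1-3 = (N − 1) × 3 / enrolment weeks:

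- N = 30: 29 × 3 / 47.7 = 1.8; 29 × 3 / 43.3 = 2.0
- N = 45: 44 × 3 / 47.7 = 2.8; 44 × 3 / 43.3 = 3.0

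Halving for an assumed 1:1 allocation (the ratio is not stated) gives 0.9-1.5 on pramipexole. These are ceilings on the expected number who step up:

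- An increase needs unsatisfactory relief.
- By the scenario tables, a subject still on one Red capsule in week 2 has no step at the end of week 2. The Section 31 prose is looser.
- The 45 includes an allowance for dropouts.

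**5. Size of one step.** Over scenarios 1-6:

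- End of week 1: 0.250/0.125 = 2
- End of week 2: 0.500/0.250 = 2
- End of week 3: 0.250/0.125 = 2, 0.500/0.250 = 2 or 0.750/0.500 = 1.5

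**The case against.** The strongest reply is that this is a deliberate choice. Section 14 addresses active subjects expressly: unanticipated risk means taper or stop, known risk means carry on. The trigger counts any grade 3 event from any cause in either arm, in chronic-pain patients on background therapy, so two unrelated or placebo-arm events would fire it. Dosing follows the manufacturer's Restless Legs titration. On hypotension the protocol reports that "the reported incidence of clinically significant orthostatic hypotension was not greater among those assigned to pramipexole tablets than among those assigned to placebo". All of this stands, and it is why the point is minor. It does not answer why no one has to look before the next increase.

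A reader might infer more than the documents support:

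- **That nobody looks at the events for a week.** The PI is told promptly, relatedness is recorded, and the adverse event procedure has the coordinator notify investigators and the HRRC with no delay stated. The first severe event will also have been reportable. What is missing is a duty to decide about other subjects' doses.
- **That two or three subjects will escalate.** That is the number in weeks 1-3, not the number stepping up.
- **That the dose could triple in one step.** One sentence describes a second titration "with the dose escalating from 0.25 mg to 0.75 mg per night", a ratio of 3, but it conflicts with the dispensing tables and is a separate inconsistency.

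The dispensing flow chart and the adverse-event script cited in Section 14 are not identifiable in the text available here. Either might contain a hold criterion. If one does, Section 14 should point to it.

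**Conclusion.** The concern holds as a minor one. As written, a second grade 3 or higher event protects future enrollees. For listed risks it leaves other subjects in weeks 1-3 with unsatisfactory relief free to take their next step without a required decision on escalation. The existing safeguards narrow the gap but impose no such decision.

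The exposure is at most about 2-3 other subjects at the time, about 1-1.5 of them on pramipexole, and at most a two-fold step by the dispensing tables. This rests on even accrual, 30-45 subjects over 10-11 months, and 1:1 allocation. The documents give no rate of grade 3 events, so the chance that the trigger fires cannot be estimated. They do not support a claim that subjects would be left without medical oversight, or that all treatment should stop after two severe events.

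**What to change.** Amend the stopping rules in Section 14 as follows.

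- A second grade 3 or higher event, or an HRRC suspension made for safety, requires a documented review by the study physician and PI before any active subject's next dose increase.
- The review uses adverse-event and dose data pooled across arms, without pain scores by arm. The 15th-participant review should not be reused for this, because it includes pain data and counts events in the active arm.
- Subjects in both arms stay at their current dose only until the review is done.
- The outcome goes to the HRRC with the existing notice.
- Continuing treatment normally does not override the dose reductions in Sections 7.5 and 14, or any HRRC instruction.

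**Cost.** One paragraph and an occasional review by existing staff. A 2-day review would catch at most 2/7 of those in weeks 1-3: 1.8 × 2/7 = 0.5 to 3.0 × 2/7 = 0.9 subjects. A subject held for the whole final week would not reach 0.75 mg. A hold applied alike in both arms does not reveal allocation, since the capsules are matched and placebo is titrated in the same way. The limit is that pooled data show dose and timing but not whether the events occurred on pramipexole.
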